8.6 Limitations

There are a couple limitations with the protocol.

Technical limitations of the system will affect the generalisability of results. At present, patients without access to any digital device would not be able to use the system and are therefore not eligible for inclusion in the study. As Wysa's algorithm is currently only compatible with the English language, non-English speaking patients will be excluded from the study, also limiting the representativeness of the sample.

Potential bias is introduced to the results by the use of qualitative interviews because of the influence of the interviewer on how participants respond (e.g. social desirability bias). This potential bias will be assessed by examining the balance of positive and negative feedback and by comparing the qualitative and quantitative data about Wysa's usability, acceptability, and impact.

8.7 Generalisability

Limitations to the generalisability of the study results were noted in the previous section. However, it is expected that the results will be generalisable to most individuals seeking general mental health support. We will also make efforts to recruit a representative sample of the UK population and include a representative subset in the semi-structured interviews.

9 ETHICAL AND REGULATORY CONSIDERATIONS

9.1 Assessment and Management of Risk and Other Ethical Issues

Standard ethical issues will be managed as follows:

- Recruitment: Participant eligibility will be determined by the screening process they undergo upon referral to IAPT. Participants who are eligible will be randomly divided by the computer into intervention and control groups with no influence from the researchers. Interview participants will also be randomly selected (from demographic groups) by a computer script of intervention users. All participants will be included in the process evaluation's quantitative analyses, thus avoiding recruitment bias.
- Power relations and other potential biases: Pre-established inclusion and exclusion criteria will be used to avoid any potential bias from the researchers as well as any coercion from participants. To prevent participation bias, only participants who would not otherwise progress down the standard care pathway will be excluded.
- Sensitivity: The outcomes measures that concern potentially sensitive topics (depression and anxiety) will be delivered to the patients' phones via the app. This allows them to avoid discussing any sensitive topics with a researcher. The semi-structured interview questions will focus only on the participants' experiences with the app (engagement and acceptability) and are intended to avoid any areas of cultural or psychological sensitivity.
- Confidentiality: To control any potential perceived issues in this area, participant confidentiality will be protected using data protection procedures that are compliant with the Data Protection Act 2018 (DPA 2018) [\[46\]](#) (as described in section 9.7).
- Timing: To mitigate any time concerns for participants, qualitative interviews will last for a maximum of 60 minutes.
- Study Governance: To maintain the integrity of the study and avoid any commercial influence, a research contract will be established between Wysa, the University of Plymouth ([name] institution), and the Institute of Cancer Research ([name] institution) that will ensure the independence of study design and execution and the unrestricted right to publish all results.
- Acceptability of study: To ensure that there are no ethical concerns with the study that might have been overlooked by the researchers and that the design is participant-friendly, a local PPI group will be formed to collaborate with researchers throughout the study. For further details, please see the PPI section.

A comprehensive risk register and Hazard log is maintained by Wysa across its development as part of its Clinical Safety Management file. This risk register will be regularly reviewed and updated as part of the project management governance. Key risks for this project include:

- Clinical: A Structured What-IF Technique (SWIFT) analysis has been completed which highlighted that the main clinical risk of this project is unintended harm. This could be psychological or physical risk caused by unintended increase in psychological distress or the physical impact of increased reliance on screen time. We have mitigated the risk to patients by building a clinically underpinned crisis response pathway with handover capabilities to the clinical team at Central North West London NHS Foundation Trust.
- Excessive screen time: Health risks associated with excessive screen time are mitigated by ensuring that many of the strategies and skills taught by the app encourage users to complete them away from the screen. All risks and mitigations are outlined in the clinical safety management file.

- Technical: The main technical risk is that the system is not fully integrated with iaptus ready for our go live date, delaying the project. This is mitigated by completing planning works and scoping prior to the application for this award and for allowing contingency time in our project planning.
- Delays: A second risk is that information governance permissions are delayed or withheld at pilot sites - mitigated by a technical, security and privacy architecture that has already been approved by the representatives of the trust who are project partners on this award.
- Commercial: The need for good quality evidence combined with long sales cycle times in healthcare can produce a risk of limited cash flow - this is mitigated by Wysa's maturity as a company and track record of securing investment funding as needed. As a real-world use study the evidence generated by the project will help to respond to commissioners' need for a high quality evidence base, removing a core barrier to implementation.

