7.5 Aims and Objectives

The primary aim of this project is to establish real-world efficacy that patient use of Wysa while waiting for treatment through the NHS mental health care pathway positively impacts well-being by comparing system users with standard services users.

The secondary aims of this project are:

1. To examine the feasibility of using Wysa to identify users at high risk of a mental health crisis and escalate them to further care;
2. To examine levels of user engagement with Wysa;
3. To evaluate patient acceptability of an autonomous early intervention supporting mental health services;
4. To complete a full health economic assessment of using Wysa for autonomous early intervention and triaging support;
5. To assess the potential for sustainable adoption of Wysa in mental healthcare pathways.

[figure not shown]

Figure 3. Wisconsin logic diagram

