Two questionnaires will be used to assess health-related quality of life: the EQ-5D-5L [40] and the Short Form 12 (SF-12) health survey [41]. The EQ-5D-5L provides a descriptive self-assessment of health in 5 dimensions: mobility, self-care, usual activities, pain/discomfort and anxiety/depression [40]. It is commonly used as a quality of life measure to conduct cost effectiveness analyses [42]. The EQ-5D-5L has a greater emphasis on physical than mental health, but has demonstrated the ability to capture changing anxiety severity [43]. The SF-12 survey is a reliable measure of functional health and is well-suited for this study, as it includes mental health items and has been shown to be acceptable for use as a screening tool for depressive disorders [44].

Cost-effectiveness

To conduct a health economic analysis, the study will collect data on health and social care service use, medication use and treatment costs, the implementation costs of Wysa, out of pocket medical expenses borne by patient and carers and productivity related costs such as work absence / time off work due illness. This data will be combined with the quality-of-life indicators to produce an assessment of the costs of adopting Wysa from the perspective of both the UK health and social care services and the wider society [45]. This analysis will also produce a budget impact model for each site that will be used to provide a final overall implementation strategy for more rapid adoption at other NHS sites and dissemination across the AHSN network in partnership with the new Integrated Care Systems. The team will also incorporate the environmental sustainability calculation in line with the Greener NHS agenda.

Table 6. Secondary Outcome Measurement

Secondary Outcome	Outcome Measure
Anxiety severity	
 Score on the GAD-7 [37]
Crisis identification	
 Number of users identified by the app for escalation of care compared to the number of patients in the control group who access A&E or out-of-hours services while waiting for treatment
Engagement	
 Uptake rates Dropout / 'did not attend' rates App usage data Qualitative feedback from semi-structured interviews
Acceptability	
 Qualitative feedback from semi-structured interviews Automated review questions periodically requested during general use of the tool

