8.3.2.2 Sampling Technique

Participants will be randomly allocated to intervention or control groups by a computer algorithm after they have provided informed consent and demographic information. Of this sample, a subset will be selected to participate in a semi-structured interview to collect qualitative data about patients' perceptions of Wysa.

To select this subset, a stratified random sampling technique will be used. Patients will be divided based on demographic characteristics (e.g. gender, age, socio-economic status, and ethnicity). From these subgroups, patients will be randomly selected so that the sample interviewed is representative of the UK population.

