8.4.3.2 Qualitative data collection

A subset of study participants will also be invited to participate in a semi-structured interview, so that more in-depth, qualitative engagement and user experience feedback can be collected. A topic guide will be developed to provide a framework for the interviews. Interviews will be conducted using video or call conferencing software and recorded for later transcription (if the participants consent). If they do not want the interview recorded, notes will be taken by hand and shared with the participant following the interview for verification. See 13.3 Appendix 3 for sample interview questions.

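### Nothing in the acceptability plan secures the views of people who never start or who abandon Wysa: the interview frame is stated three ways, is stratified by demographics only, and is paired with in-app prompts

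*Protocol*

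**What the plan says.** Secondary aim 3 in Protocol 7.5 is patient acceptability. Aim 5 is "To assess the potential for sustainable adoption of Wysa in mental healthcare pathways". Section 7.3 assigns long-term adoption to a framework built around non-adoption and abandonment.

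Table 6 in 8.2.5.2 gives acceptability two sources. One is qualitative feedback from interviews. The other is "Automated review questions periodically requested during general use of the tool".

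Who may be interviewed is stated in three places:

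- 9.1: "Interview participants will also be randomly selected (from demographic groups) by a computer script of intervention users".
- 8.3.2.2, directly after describing random allocation: "Of this sample, a subset will be selected to participate in a semi-structured interview".
- 8.4.3.2: "A subset of study participants will also be invited to participate in a semi-structured interview".

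On strata, 8.3.2.2 says "Patients will be divided based on demographic characteristics", with gender, age, socio-economic status and ethnicity as examples. The stated purpose is a draw made "so that the sample interviewed is representative of the UK population". No section mentions app use as a basis for selection. Appendix 3 lists seven sample questions, all about interacting with or understanding Wysa.

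The plan also measures uptake, dropout and app usage (8.2.5.2) and puts all participants into the quantitative part of the process evaluation (9.1). The SAP does not mention acceptability or the interviews.

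**The concern.** People who never open an app, or leave it early, are those most likely to have found it unappealing, unclear or unsuitable. An acceptability study that hears mainly from people who kept using it will tend to give a more favourable picture. It will also lack the information that an adoption assessment most needs, namely why people did not take the app up or gave it up.

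Here the in-app source is selected by use from the start. The interviews could correct for this, but their frame is unclear and their strata ignore use. The results feed an implementation strategy for other NHS sites (8.2.5.2, 10.1), so a gap in the reasons for non-adoption would carry forward. The primary PHQ-9 comparison is untouched.

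**Working it through.** No figure in the documents bears directly on this point: the number of interviews, expected uptake and expected app dropout are not given. The check is therefore a comparison of the passages, followed by an illustration on labelled assumptions.

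**1. Who each source can reach**

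| Source | Never started | Tried and stopped |
|---|---|---|
| In-app review questions (Table 6) | not reached | not reached once they stop |
| Interviews, 9.1 read literally | outside the frame | in the frame, by chance |
| Interviews, 9.1 read as the allocated arm | in the frame, by chance | in the frame, by chance |
| Interviews, 8.3.2.2 or 8.4.3.2 | in the frame, by chance (controls too) | in the frame, by chance |

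Only one reading excludes never-starters from interview, and none excludes people who tried and stopped. Equally, no reading gives either group a stratum or quota. The wider frames in 8.3.2.2 and 8.4.3.2 also take in control participants, who receive the app only after the control period (8.3.3.1).

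**2. Whether the questions fit**

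All seven questions in Appendix 3 presuppose some contact with Wysa. Someone who stopped could answer those on effort, concerns and losses. Someone who never started could answer very little. None asks why a person did not begin or gave up.

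**3. Whether the planned bias checks cover it**

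Section 8.6 names interviewer influence as the source of bias. Its first check, the balance of positive and negative feedback, says nothing about people who were not asked. Its second check compares qualitative with quantitative data. That could expose a mismatch, such as warm interviews beside poor uptake, but it would not supply the reasons.

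**4. Illustration of what a demographic-only draw gives**

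Assumptions: 20 interviews; a share q of 10% to 50% of the intervention arm never starts. Arm size N is 480/3 = 160 under the ratio in Protocol 8.3.2.1, or 480 × 2/3 = 320 under the opposite ratio in the SAP (a separate matter).

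- *9.1 read literally.* People outside the frame = q × N: 16 to 80 of 160, or 32 to 160 of 320.
- *Whole arm as frame, everyone invited takes part.* Expected never-starters = 20q = 2 to 10. With m = qN, the chance of drawing none is C(N − m, 20)/C(N, 20). At q = 10% this is 0.105 (N = 160) or 0.113 (N = 320); at q = 20% it is 0.008 or 0.010, and it falls further above that.
- *Whole arm as frame, unequal response.* Suppose 50% of users accept, against r = 10% or 25% of never-starters. Their share of interviewees is qr/[qr + (1 − q) × 0.50]. For q = 10%, r = 10%: 0.010/(0.010 + 0.450) = 0.022.

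| q | r = 10% | r = 25% |
|---|---|---|
| 10% | 2.2% | 5.3% |
| 30% | 7.9% | 17.6% |
| 50% | 16.7% | 33.3% |

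Never-starters would be about 2% to 33% of interviewees instead of 10% to 50%. In 20 interviews that is 20 × 0.022 ≈ 0.4 to 20 × 0.333 ≈ 6.7 people. How far they are under-represented depends on the frame and on response, and the protocol fixes neither.

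**The case against.** The strongest reply is that the frame is not shown to exclude anyone. The protocol uses the word users loosely: 7.5 and 8.2.5.1 describe the primary comparison in terms of users of the app, yet 8.5.1 analyses by intention to treat. In 9.1 the phrase comes soon after a mention of the intervention and control groups, so it may simply mean the intervention arm. This stands. Exclusion of never-starters is one reading, not an established fact.

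A reader might go further and infer that both aims will be answered only by people who persisted with the app. The documents do not support that. No section makes continued use a condition of interview, so people who tried Wysa and stopped can be drawn. Uptake, dropout and usage are measured, so the extent of non-use will be known. The adoption framework covers individuals and systems, and cost and budget-impact work also informs the adoption strategy.

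A reader might also want to state the overstatement in percentage points. That would need assumed rates of non-use and of approval in each group. The interviews, moreover, are to be analysed thematically (8.5.2), with no proportion planned from them.

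Two smaller points also stand. Appendix 3 is only a sample, and 8.4.3.2 says the guide is still to be developed. Figures 4 and 5, which may show who is approached and when, are not visible in the text available.

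None of this supplies a mechanism for hearing from non-starters or early leavers. The in-app limitation holds under every reading, and three differing statements of the frame need reconciling in any case.

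**Conclusion.** The point holds as a gap in what the plan secures. Reasons for non-uptake and abandonment, needed for aims 3 and 5, may go unobserved, and acceptability is likely to look more favourable than it is. The direction rests on the assumption that people who did not start or who stopped hold less favourable views on average, which is plausible but not stated in the documents. The size cannot be derived. The figures above show only how the make-up of the interview sample could shift under assumed non-use and response rates, and are not estimates of bias.

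This is a worthwhile, inexpensive improvement to a secondary, mainly qualitative part of the trial. It has no bearing on the primary analysis.

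**What to change.** 1. Reconcile 8.3.2.2, 8.4.3.2 and 9.1 so that all three give one interview frame: everyone allocated to Wysa, whether or not they opened it.
2. Add an engagement stratum from the app-use data that 8.4.3.1 says is stored automatically: never started, stopped early, sustained use. Define the cut-offs before drawing, and draw from each stratum within the planned number of interviews. Non-users can be reached through the email address required at entry or by phone.
3. Add questions to the guide that someone who never started, or who left, can answer. Make sure that the description of interview content in 9.1, which is confined to experience of the app, allows them.
4. Report invitations and responses by use group.
5. Report in-app review scores with the number responding out of the number allocated, and describe them as the views of continuing users.

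The cost is revised sampling text and an adapted guide, with no increase in interviews. Non-users may accept less often, so some replacement invitations will be needed, and each demographic cell will hold slightly fewer interviews. The SAP is dated 8 August 2023 and describes randomisation as done. If the interviews are also complete, items 4 and 5 still apply, and the limitation should be stated beside the acceptability and adoption findings.

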9.2 Research Ethics Approval

The study protocol will undergo institutional and regulatory review and approval prior to commencement. To ensure that our data reporting is in line with NHS standards we will be following the Department of Health and Social Care guidelines for good practice for digital and data driven health technologies [47]. As per the guidelines, we will be applying the Caldicott Principles for the collection and evaluation of patient data and everyone dealing with patient information will be required to complete the online training prior to starting on the project to evidence familiarity with these.

Ethical approval is being sought from the Health Research Authority and the relevant Research Ethics Committee with this submission [48]. As the IRAS system brings together these assessments, only one application is needed [48]. The protocol will therefore receive medical device review from the associated REC.

Additional independent ethical approval will be sought from the University of Plymouth. At the University of Plymouth, an application for ethical approval will be submitted through the Plymouth Ethics Online System to the Health Faculty Research Ethics and Integrity Committees (FREIC) [49].

The University of Plymouth, as the study sponsor, will ensure that the study has received ethics approval from a research ethics committee (REC) and has received Health Research Authority (HRA) approval.

9.3 Peer Review

The study will undergo peer review and ethical approval via the University of Plymouth research governance process.

9.4 Patient and Public Involvement

The CNWL NHS Foundation Trust, SW AHSN, and Institute of Cancer Research have robust PPI support infrastructures to ensure we are able to have the necessary support in place to establish our PPI framework for the research study. Partnerships with both of these institutions will ensure we align our PPI practices as we move through the research cycle. A PPI lead for the study has been recruited and is working with a number of PPI engagement groups at CNWL to support the trial.

9.4.1 Involving a lay representative on the study monitoring group

A lay representative will be appointed to the study monitoring group, additional the patient representative will be invited to key strategic and public meetings. The lay representative will be involved in all aspects of the study, specifically, these include, but are not restricted to review of

each milestone and acceptance of deliverables - seeking their views around acceptability of patient-facing materials, study procedures, and plans for translation to clinical practice.

9.4.2 Involving a dedicated PPI group

The broad aims of the PPI group are to support the governance of patient and public involvement and engagement approaches and activities within this study and ensure the public voice is present through all stages of the research cycle. Membership of the PPI group will be open to those both with a direct interest in telemedicine or mental health, but also any lay member with an interest in our broader aims. We will include patients and lay members both with and without previous experience of PPI to make sure we have a variation of skills and expertise.

We will form a bespoke PPI group for the project including existing members of the Wysa PPI community as well as members of the CNWL PPI community who are interested in progressing the use of AI in population access to mental health. We will hold a number of experience-based co-design (EBCD) workshops using storyboarding and community asset mapping to establish design and preference mapping and the group will also provide final sign off at milestone achievements in the work packages.

With input from the Imperial College PERC, we have drafted, based on NIHR Involve guidance, a term of reference, confidentiality agreement and a background assessment form to allow us to realise the broad aims of our PPI group. Membership of this Wysa PPI group is voluntary but requires members to be committed to attend meetings and to respond to emails/ correspondence. The initial term of membership is for the duration of the study from early in the preparation phase (app. Dec 2021 / Jan 2022). We aim to have a minimum of four formal members at the inception of the panel and each subsequent meeting with representation from both London and the Southwest. We will seek to make participation as diverse as possible by selecting members based on 1) demographics 2) levels of PPI experience and 3) connection to telemedicine or mental health based on the results of our basic background form. We are aware that we have to ensure Wysa's product is as accessible to as wide a range of possible demographics as possible, and the first phases of setting up our PPI group will involve a wide search using networks from SW AHSN and NIHR Involve's "People in Research" platforms.

The panel will aim to convene every four months for a 90-minute formal group discussion, given the evolving Covid-19 situation, we anticipate at least some of these group discussions to be conducted via video-conferencing, with more informal discussions happening via email or phone-calls. As the study spans two sites, we envision using teleconferencing to help enable maximal participation of our participants and to lower the barriers to involvement. At both sites, a dedicated location for teleconferencing will be designated to ensure we are not excluding participants less comfortable with or less willing to use technology.

We anticipate that we will be having an ongoing dialogue with study participants both formally in the afore-described evaluation phase, and informally via ongoing feedback. As such, we anticipate that new members may be recruited to the PPI group if there are gaps in experience. The panel may choose to invite other patients/members of the public involved; other university members and/or representatives of voluntary or community organisations on a one/off or long-term basis. Observers, guests and presenters may also be invited on a one/off basis.

The meetings will be co-chaired by a lay chairperson who is nominated by all attendees of the meeting, and a professional chairperson will be a senior Wysa team member who has received formal experience in chairing PPI meetings. We have drafted a "role" specification with Imperial PERC of a chairperson which may be a different individual between meetings depending on topics of discussion.

Payments will be made in recognition of members' time based on NIHR Involve guidance on payment of fees and expenses for our members actively involved [50]. Travel expenses will be reimbursed in accordance with this policy together with other expenses and travel costs. We have budgeted based on suggested reimbursement schedules and have produced our estimates following use of the Involvement Cost Calculator.

